5.1.1. Selection of communities and households

This study will enrol subjects in selected communities based on the following non-exclusive characteristics:

- preferably in areas where access to the community is already established (previous community-based surveillance studies)
- in areas with a high population density
- in areas with low out-migration rate
- in areas with preferably a single point-of-care for the community
- preferably in areas where there is a confirmation of dengue endemicity
- in areas where children are likely to constitute at least 30% of the study population per site
- in households with at least one child (less than 18 years of age)
- in households with at least one adult (aged no more than 50 years) and one child (aged less than 18 years) consenting (and assenting if applicable) to participate in the study

Refer to Section 5.1.2 for an overview of the recruitment plan.
(Amended 01 March 2017).

A list of all households in the sampling area will be generated by each site. Simple random sampling will be performed to select households for enrolment. If the sampling area is too large to compile a list of all households, at least eight clusters of similar population size (blocks or streets) will be selected by simple random sampling. Households in the selected clusters will then be listed and selected by simple random sampling.

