Issue diary cards to subjects/subject's parent(s)/LAR(s) to be filled out in the event of fever ⁶	○	○	○
Record SAEs related to study participation	●	●	●
Study conclusion ⁷			●

● is used to indicate a study procedure that requires documentation in the individual eCRF.

○ is used to indicate a study procedure that does not require documentation in the individual eCRF.

μPRN: micro-plaque-reduction neutralisation; **eCRF:** electronic Case Report Form; **ELISA:** enzyme-linked immunosorbent assay; **ICT:** immunochromatographic; **JEV:** Japanese encephalitis virus; **LAR:** legally acceptable representative; **NS1:** non-structural protein 1; **RT-qPCR:** reverse transcriptase quantitative polymerase chain reaction; **SAE:** serious adverse event. (Amended 01 March 2017)

* Blood samples should only be drawn in case of AFI (i.e., fever [body temperature $\geq 38^{\circ}\text{C}/\geq 100.4^{\circ}\text{F}$] on ≥ 2 consecutive calendar days, measured **at least twice**, at least 8 hours apart) during the Suspected Dengue First Visit from the second day of fever (i.e., from Day 2, the second calendar day with fever) and onwards, up to Day 7.

- 1) A Return Visit is a visit linked to the Suspected Dengue First Visit and should take place if the subject's physical condition necessitates medical evaluation, according to local medical practice. The investigator will determine whether this Return Visit is necessary and whether it is considered as part of the same episode.
- 2) A Suspected Dengue Follow-up Visit may occur during a weekly home visit. This visit should be performed by a medically trained site staff member. ***Note that when a subject comes in for a suspected dengue follow-up visit, this will replace the regularly scheduled weekly home visit.*** (Amended 01 March 2017)
- 3) For all subjects ≥ 5 years of age. For subjects < 5 years of age only if clinically indicated, as per investigator judgement. Complete blood count (White blood cells [WBC], red blood cells [RBC], platelets and haemoglobin).
- 4) For subjects ≥ 18 years of age only. Including, but not limited to, neutralising antibody against JEV and Chikungunya virus. A subset of samples will be tested.

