6.5.5.1.4. Blood sampling

Blood samples should only be drawn in case of AFI (i.e., fever [body temperature $\geq 38^{\circ}\text{C}/\geq 100.4^{\circ}\text{F}$] on ≥ 2 consecutive calendar days, measured at least twice, at least 8 hours apart) during the Suspected Dengue First Visit from the second day of fever (i.e., from Day 2, the second calendar day with fever) and onwards, up to Day 7.

The following blood samples should be collected unless an obvious alternative diagnosis, i.e., an obvious cause of fever other than dengue, has been identified and is documented (Amended 01 March 2017):

- Whole blood for laboratory confirmation of dengue by NS1-antigen (ICT test and/or ELISA): 0.5 mL, from all subjects (any age). The results of this/these test(s) should be recorded in the eCRF.
- Whole blood for laboratory confirmation of dengue infection by (generic and/or serotype-specific) RT-qPCR: 2.5 mL, from all subjects (any age).

- Whole blood for haematology assessment (complete blood count): 2 mL, from all subjects \geq 5 years of age and from subjects $<$ 5 years of age only if clinically indicated, as per investigator judgement or local recommendations. The results of these tests should be recorded in the eCRF.
- Whole blood for other tertiary (research) endpoints related tests (including, but not limited to, neutralising antibody against JEV and Chikungunya virus, tissue culture to isolate infectious agents, and sequencing to characterise infectious agents): **3.5 mL**, from all subjects \geq 18 years of age. A subset of these samples will be tested.

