9.1.3. Tertiary (research) endpoints

During the Suspected Dengue First Visit, additional blood volumes will be collected for tertiary study endpoint assays. These tertiary study endpoints include, but are not limited to, determination of neutralising antibody titres against dengue virus (DENV), Japanese encephalitis virus (JEV), and chikungunya virus, tissue culture to isolate infectious agents, and sequencing to characterise infectious agents. **(Amended 01 March 2017)**

Tertiary study endpoint assays *may* be performed for a subset of samples (for example, JEV assays will only be conducted if additional studies indicate that JEV serology is needed to interpret the DENV antibody response), i.e., not all of these endpoint assays will be performed on all of the sera collected from adult study subjects. **(Amended 01 March 2017)**

Research objectives may be assessed based on, but not limited to, the following endpoints: **(Amended 01 March 2017)**

- Neutralising antibody titres against JEV.
- Neutralising antibody titres against other viruses, including but not limited to, Chikungunya virus.
- Incidence of NS1-antigen (ICT test and/or ELISA)-positive AFI by DENV type.
- Concordance between dengue RT-qPCR and NS1-antigen (ICT and/or ELISA) assays.
- Occurrence of AFI due to LCD and due to non-LCD having (\geq 3 days of fever (body temperature (\geq 38°C/ \geq 100.4°F).
- Occurrence of AFI due to LCD and due to non-LCD resulting in hospitalisation.
- Occurrence of combinations of signs and symptoms during the 7-day period following the onset of each episode of AFI due to LCD and due to non-LCD.
- Occurrence of AFI due to LCD within 2 weeks from an index case, in the same household or within 50 metres of the household of the index case.
- Entomological characteristics for LCD cases (e.g., vector species, density and number of breeding sites) at selected site(s).
- Occurrence (by medical history only) of a diagnosis of tuberculosis, from birth up to study conclusion, in the study population.
- Occurrence of hospitalisation and discharge diagnosis.
- Identification and characterisation of infectious agents isolated from blood (e.g., DENV, influenza viruses, chikungunya viruses), in subjects with AFI.

Please refer to Section 4 for the case definitions of AFI due to LCD and due to non-LCD.

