5.4. Tertiary objectives

5.4.1. Analysis of tertiary objectives planned in the protocol

- Sensitivity, specificity, positive predictive value, negative predictive and overall agreement value of NS1-antigen (ICT test) in prediction of RT-qPCR test results will be computed. Cohen's Kappa will be used to evaluate the agreement between two measures. See section 9.2.3.
- Computation of incidence rate of AFI due to dengue confirmed by NS1-antigen (ICT test and/or ELISA) with 95% CI: the numerator will be the number of subjects with AFI due to dengue confirmed by NS1-antigen (ICT test and/or ELISA) during the study period. The denominator will be the total person-years at risk.
- Computation of incidence rates of AFI due to LCD having ≥ 3 consecutive calendar days of fever (body temperature $\geq 38^{\circ}\text{C}/\geq 100.4^{\circ}\text{F}$) and incidence of AFI due to LCD resulting in hospitalisation with 95% CI.
- Frequency of symptoms associated with AFI due to LCD having ≥ 3 consecutive calendar days of fever (body temperature $\geq 38^{\circ}\text{C}/\geq 100.4^{\circ}\text{F}$) and result in hospitalization will tabulated overall and by age group. Univariate and Multivariate analyses will be done to identify categories of medically relevant signs and symptoms associated with high probability of LCD (any severity, having ≥ 3 consecutive calendar days of fever (body temperature $\geq 38^{\circ}\text{C}/\geq 100.4^{\circ}\text{F}$) and resulting in hospitalisation) *versus* non-LCD episodes using logistic regressions. See section 9.2.4.
- Computation of the frequency and percentage of the reasons of hospitalization throughout the study among all hospitalization visits.
- Calculation of the frequency and percentage of subject with other infective agent: influenza viruses, chikungunya viruses among subject with subjects with AFI.

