8. CHANGES FROM PLANNED ANALYSES

Due to limitations of data (no data availability) or resources, the following tertiary objectives are omitted from the analysis.

- To describe DENV and Japanese Encephalitis Virus (JEV) antibody profiles in subsets of subjects with AFI.
- Neutralising antibody titres against DENV 1-4.
- Neutralising antibody titres against JEV.
- Neutralising antibody titres against other viruses, including but not limited to, Chikungunya virus.
- To describe spatio-temporal clustering of LCD cases.
- To describe entomological characteristics at selected site(s).
- To estimate the prevalence and incidence of tuberculosis diagnosis in the study population.
- To isolate and characterise infectious agents from a subset of subjects with AFI.
- To evaluate the antibody response to infectious agents in a subset of subjects with AFI.

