10.1.1.2. Laboratory data

Missing laboratory results (including immunological data) will not be replaced.

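### SAP 5.4.1 keeps an influenza and chikungunya percentage whose objectives Section 8 drops, over a denominator that includes subjects who were never tested

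*SAP*

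**What the plan says.** SAP 5.4.1, among the tertiary analyses, lists: "Calculation of the frequency and percentage of subject with other infective agent: influenza viruses, chikungunya viruses among subject with subjects with AFI". The denominator is subjects with AFI. Nothing restricts it to subjects sampled, tested or with a valid result.

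SAP Section 8 lists tertiary items omitted because data or resources are lacking. One is "To isolate and characterise infectious agents from a subset of subjects with AFI". It also omits the evaluation of antibody response to infectious agents, and neutralising titres against other viruses, with chikungunya named.

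The protocol limits who can have a result:
- Table 3 in Section 6.4 restricts the 3.5 mL research sample: "For subjects ≥ 18 years of age only".
- Section 6.5.5.1.4 says of that sample: "A subset of these samples will be tested".
- Section 9.1.3 adds that "not all of these endpoint assays will be performed on all of the sera collected from adult study subjects".
- Section 6.5.5.1.4 also says that blood samples "should be collected unless an obvious alternative diagnosis" has been found and documented.

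**The concern.** Two things look wrong. First, one section of the SAP instructs the programmer to produce a table whose supporting objectives another section drops. Both are current text of the same document, and Section 8 does not name the 5.4.1 bullet, so a programmer could reasonably follow either.

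Second, if the table is produced, subjects who had no chance of a positive result sit in the denominator. The percentage then mixes how often the agent was found with how many subjects were tested, and a reader of the report cannot separate the two. At stake is a misleading account of which other agents cause fever in this cohort. In the extreme case a zero would appear where the honest entry is that no test was done.

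**Working it through.** The documents state no figure for this percentage, so there is nothing to reproduce. The check compares the sections and then works out what the written rule returns.

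**1. Where a result could come from.** Protocol 9.1.3 offers two routes to an influenza or chikungunya result: agents isolated from blood and characterised (both viruses are given as examples), and neutralising antibody against other viruses (chikungunya is named). Table 14 in Protocol 6.8 matches this with tissue culture, sequencing and viral serology. SAP Section 8 omits the isolation objective, the antibody-response objective and the titres. Both routes are therefore dropped while the 5.4.1 bullet remains.

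**2. Who can enter the numerator if the bullet is run.** Only subjects aged 18 or over give the research sample, and only some of those samples are tested. AFI with an obvious alternative diagnosis need not be sampled, yet it remains an AFI case, classed as undetermined under Protocol 4.3. Enrolment starts at 6 months of age, and communities are sought "in areas where children are likely to constitute at least 30% of the study population per site". Children with AFI are thus in the denominator but cannot be in the numerator.

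**3. What the rule returns.** Let
- p = proportion positive among tested subjects,
- a = adult share of subjects with AFI,
- f = fraction of adults with AFI who are tested.

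With N subjects with AFI, the number tested is N × a × f and the number positive is N × a × f × p.
- Over all subjects with AFI: (N × a × f × p) / N = p × a × f.
- Over tested subjects: (N × a × f × p) / (N × a × f) = p.

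The ratio of the two is a × f, whatever the value of p. It is below 1 as soon as one child or one untested adult has AFI.

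The documents give none of p, a or f. Taking p = 10% purely as an assumption:

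| a (assumed) | f (assumed) | a × f | Over all AFI | Over tested |
|---|---|---|---|---|
| 0.7 | 1.0 | 0.70 | 7.0% | 10% |
| 0.7 | 0.5 | 0.35 | 3.5% | 10% |
| 0.7 | 0.25 | 0.175 | 1.75% | 10% |
| 0.5 | 0.5 | 0.25 | 2.5% | 10% |
| 0.3 | 0.25 | 0.075 | 0.75% | 10% |

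Over a from 0.3 to 0.7 and f from 0.25 to 1.0, the reported figure is 7.5% to 70% of the percentage among those tested. If nobody is tested (f = 0), the rule returns 0 / N = 0%, whereas the percentage among tested subjects is undefined.

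**4. Whether another rule removes untested subjects.** SAP 10.1.1.2 says "Missing laboratory results (including immunological data) will not be replaced". That bars imputation; it does not redefine a denominator stated as subjects with AFI. Protocol 9.4 does exclude subjects with missing measurements, but within the rule for immunogenicity measurements and geometric mean titres, and the SAP does not carry it over. Protocol 9.7 describes no analysis of other infectious agents, so it supplies no denominator either.

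**The case against.** The strongest reply is that the analysis will not be run. SAP 3.6 sends the reader to Section 8 for tertiary analyses that are not performed, and Section 8 drops the inputs. On that view the bullet is a leftover and no biased figure will appear. This stands to a large extent, and it is why the conflict comes first in this point. It does not make the text harmless, because 5.4.1 still orders the calculation.

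A second reply is that the bullet is garbled, that the objective itself speaks of a subset, and that table denominators may be set in the separately filed tables document (SAP 10.2), which is not available here. The programmer may well intend a tested-only denominator. That is possible, but the SAP does not say so.

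A third reply concerns direction. A reader might infer that the percentage must understate the share of fevers due to these agents. The documents do not support that without conditions. The protocol's chikungunya serology is neutralising antibody, on blood drawn only at the Suspected Dengue First Visit. Antibody in one acute sample may reflect past infection, which pushes the figure up. The downward direction holds for virus detected directly by a specific method.

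A fourth reply is that testing a subset gives no unbiased share either. The selection rule is not stated. If samples were picked on clinical suspicion or because dengue was negative, positivity among those tested could exceed that among all adults with AFI. This stands, and the fix has to cover it.

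**Conclusion.** The inconsistency between SAP 5.4.1 and Section 8 is real and needs reconciling. If the analysis is kept, the denominator of all subjects with AFI is wrong as written: it dilutes the percentage with directly detected virus by the fraction of AFI subjects tested.

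The size of the dilution cannot be computed from the documents. A reader might take the 30% child share as the untestable share of AFI subjects. It is a site-selection characteristic of the enrolled population, and the age mix of AFI subjects is not given. The tabulated values show only how the rule behaves under assumed inputs; they do not measure an error in this study.

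The conclusion assumes that the denominator is applied as worded and that a positive result means current infection. The consequence is small: one descriptive percentage under a tertiary objective, with the primary and secondary analyses untouched.

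**What to change.** Choose one:

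- **Drop the analysis.** Delete the bullet from SAP 5.4.1 so that it agrees with Section 8, and name in Section 8 the matching endpoint still listed in 3.6.
- **Keep the analysis.** Correct Section 8 to say which results exist. In 5.4.1, set the denominator separately for each agent as subjects with AFI who have a valid result for that agent. Report the number tested over the number with AFI, state how the tested subset was chosen, and label the result as applying to tested adults only. Present virus detection and antibody separately, and do not interpret antibody positivity in a single acute sample as the cause of the fever.

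Deletion costs a line or two of SAP text. Keeping it costs a few sentences and a table footnote. Neither needs new data collection.

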6. ANALYSIS INTERPRETATION

All analyses are descriptive. The use of these descriptive analyses should be limited to supportive analysis of confirmatory analyses or hypothesis generation.

7. CONDUCT OF ANALYSES

7.1. Sequence of analyses

Description	Analysis ID	Disclosure Purpose (CTRS=public posting, SR=study report, internal)	Dry run review needed (Y/N)	Study Headline Summary (SHS)requiring expedited communication to upper management (Yes/No)	Reference for TFL
Final Analysis	E1_01	SR	No	No?	DPIV-021 EXPLO (200274) TFL

8. CHANGES FROM PLANNED ANALYSES

Due to limitations of data (no data availability) or resources, the following tertiary objectives are omitted from the analysis.

- To describe DENV and Japanese Encephalitis Virus (JEV) antibody profiles in subsets of subjects with AFI.
- Neutralising antibody titres against DENV 1-4.
- Neutralising antibody titres against JEV.
- Neutralising antibody titres against other viruses, including but not limited to, Chikungunya virus.
- To describe spatio-temporal clustering of LCD cases.
- To describe entomological characteristics at selected site(s).
- To estimate the prevalence and incidence of tuberculosis diagnosis in the study population.
- To isolate and characterise infectious agents from a subset of subjects with AFI.
- To evaluate the antibody response to infectious agents in a subset of subjects with AFI.

9. NON-STANDARD DATA DERIVATION RULES AND STATISTICAL METHODS

9.1. Data derivation

9.1.1. Case Definition

The different case definitions for febrile illness are summarized in Table 2

Table 2 Summary of case definitions

Endpoint	Case definition	Case definition for ad-hoc Analysis
AFI with LCD	
[Fever (body temp \geq 38 C /100.4 F) on at least 2 consecutive days are measured at least twice, at least twice 8 hours apart
 
AND
 
Dengue RT-qPCR result on the acute serum sample taken during the 7-day period from onset of fever is positive
	
[Fever (body temp \geq 38 C /100.4 F) on at least 2 consecutive days are measured at least twice, OR
 
Fever (body temp \geq 38 C /100.4 F) on at least 1 day is measured at least twice 8 hours apart
 
AND
 
Clinical suspicion of dengue base on solicited symptoms],
 
AND
 
Dengue RT-qPCR result on the acute serum sample taken during the 7-day period from onset of fever is positive

DENV – 1 LCD	
[Fever (body temp \geq 38 C /100.4 F) on at least 2 consecutive days are measured at least twice, at least twice 8 hours apart
 
AND
 
Dengue 1 specific RT-qPCR result during the 7-day period from fever is positive
	
[Fever (body temp \geq 38 C /100.4 F) on at least 2 consecutive days are measured at least twice, OR
 
Fever (body temp \geq 38 C /100.4 F) on at least 1 day is measured at least twice 8 hours apart
 
AND
 
Clinical suspicion of dengue base on solicited symptoms],
 
AND
 
Dengue 1 specific RT-qPCR result during the 7-day period from fever is positive

Endpoint	Case definition	Case definition for ad-hoc Analysis
DENV – 2 LCD	
[Fever (body temp \geq 38 C /100.4 F) on at least 2 consecutive days are measured at least twice, at least twice 8 hours apart
 
AND
 
Dengue 2 specific RT-qPCR result during the 7-day period from fever is positive
	
[Fever (body temp \geq 38 C /100.4 F) on at least 2 consecutive days are measured at least twice, OR
 
Fever (body temp \geq 38 C /100.4 F) on at least 1 day is measured at least twice 8 hours apart
 
AND
 
Clinical suspicion of dengue base on solicited symptoms], AND
 
Dengue 2 specific RT-qPCR result during the 7-day period from fever is positive

DENV – 3 LCD	
[Fever (body temp \geq 38 C /100.4 F) on at least 2 consecutive days are measured at least twice, least twice 8 hours apart
 
AND
 
Dengue 3 specific RT-qPCR result during the 7-day period from fever is positive
	
[Fever (body temp \geq 38 C /100.4 F) on at least 2 consecutive days are measured at least twice, OR
 
Fever (body temp \geq 38 C /100.4 F) on at least 1 day is measured at least twice 8 hours apart
 
AND
 
Clinical suspicion of dengue base on solicited symptoms], AND
 
Dengue 3 specific RT-qPCR result during the 7-day period from fever is positive

DENV – 4 LCD	
[Fever (body temp \geq 38 C /100.4 F) on at least 2 consecutive days are measured at least twice, at least twice 8 hours apart
	
[Fever (body temp \geq 38 C /100.4 F) on at least 2 consecutive days are measured at least twice, OR

Endpoint	Case definition	Case definition for ad-hoc Analysis
	
AND
 
Dengue 4 specific RT-qPCR result during the 7-day period from fever is positive
	
Fever (body temp ≥ 38 C /100.4 F) on at least 1 day is measured at least twice 8 hours apart
 
AND
 
Clinical suspicion of dengue base on solicited symptoms], AND
 
Dengue 4 specific RT-qPCR result during the 7-day period from fever is positive

Non LCD	
[Fever (body temp ≥ 38 C /100.4 F) on at least 2 consecutive days are measured at least twice, at least twice 8 hours apart
 
AND
 
Dengue RT-qPCR result during the 7-day period from fever is negative
	
[Fever (body temp ≥ 38 C /100.4 F) on at least 2 consecutive days are measured at least twice, OR
 
Fever (body temp ≥ 38 C /100.4 F) on at least 1 day is measured at least twice 8 hours apart
 
AND
 
Clinical suspicion of dengue base on solicited symptoms], AND
 
Dengue RT-qPCR result during the 7-day period from fever is negative

Undetermined	
[Fever (body temp ≥ 38 C /100.4 F) on at least 2 consecutive days are measured at least twice, at least twice 8 hour apart
 
AND
 
Dengue RT-qPCR result during the 7-day period from fever is invalid or missing
	
[Fever (body temp ≥ 38 C /100.4 F) on at least 2 consecutive days are measured at least twice, OR
 
Fever (body temp ≥ 38 C /100.4 F) on at least 1 day is measured at least twice 8 hour apart

Endpoint	Case definition	Case definition for ad-hoc Analysis
		AND Clinical suspicion of dengue [base on solicited symptoms], AND Dengue RT-qPCR result during the 7-day period from fever is invalid or missing

